### **Vaccine Group Labelling in TFLs:**

The table below outlines the Vaccine Groups labeling for all Tables, Listings and Figures (wherever as appropriate):

Group 1	Group 2	Group 3	Group 4
100µg Na -GST-1/Alhydrogel®	100µg Na -GST-1/Alhydrogel® plus 500µg CpG 10104	100µg Na -GST-1/Alhydrogel® plus 5µg AP 10-701	Placebo

### **5.2 Definition**

**Baseline:** Baseline is defined as the latest non-missing assessment (whether from scheduled or unscheduled) prior to the first dose administration of the study vaccine, unless otherwise stated.

The **Post-baseline** values are defined as measurements taken after the first administration of study product.

**Change from Baseline:** The change from baseline values will be calculated as post baseline value minus the baseline value.

**An Adverse Event** is any untoward medical occurrence in a subject or clinical investigation in a subject administered a pharmaceutical product and which does not necessarily have to have a causal relationship with this vaccination. An adverse event can be any unfavorable sign (including an abnormal laboratory finding), symptom, or disease temporally associated with the use of the investigational product, whether considered related or not related to the investigational product.

A pre-vaccination condition is any event in a clinical study subject that occurs after he/she signed the Informed Consent Form (ICF) up until the first administration of study vaccine. All pre-vaccination conditions will be considered as medical history whereas any pre-vaccination condition that worsens after vaccination will be considered as an AE.

**An SAE** is any AE that results in death, is life-threatening (this refers to an event in which the subject was at risk of death at the time of the event; it does not refer to an event that hypothetically might have caused death had it been more severe), requires inpatient hospitalization or prolongation of existing hospitalization, results in persistent or significant disability/incapacity, is a congenital anomaly/birth defect, requires medical or surgical intervention to prevent any of the occurrences noted above.

**Unexpected Adverse Event:** Any adverse event, the specificity or severity of which is not consistent with the current Investigator's Brochure.

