**Description of Study Design:**

Double blind, randomized, controlled, Phase 2 clinical trial in hookworm-unexposed adults living in the metropolitan area of Washington, DC. Subjects will receive three doses of the assigned vaccine formulation, or saline placebo, delivered intramuscularly on approximately Days 0, 56, and 112.

Subjects will be challenged with 50 infectious *N. americanus* larvae 4 weeks after 3rd vaccination. Subjects will be evaluated weekly starting 5 weeks post-challenge to assess infection status. Albendazole will be administered 20 weeks post-challenge to cure infections. Subjects will be followed until 10 months after their final vaccination.

Safety of vaccination will be measured from the time of each study vaccination (Day 0) through 14 days after each study vaccination by the occurrence of solicited injection site and systemic reactogenicity events. Safety of CHHI will be measured from the time of larval application (Day 140) through the first day of treatment with albendazole (Day 280).

Unsolicited non-serious adverse events (AEs) will be collected until approximately 1 month following each study vaccination and from study Day 140 (day of CHHI) through Day 297.

New-onset chronic medical conditions, Serious Adverse Events (SAEs), and Adverse Events of Special Interest (AESIs) will be collected from the time of the first study vaccination through approximately 10 months after the third study vaccination (final visit). Clinical laboratory evaluations for safety will be performed on venous blood collected approximately 14 days after each vaccination and CHHI.

Immunogenicity testing will include IgG antibody responses to Na-GST-1, by a qualified indirect enzyme-linked immunosorbent assay (ELISA), on serum obtained prior to each study vaccination and CHHI, and at time points after each vaccination and after CHHI (see Appendix A); the affinity of vaccine-induced antibodies against Na-GST-1 using Surface Plasmon Resonance; the functional activity of vaccine-induced antibodies via *in vitro* enzyme neutralization assay; antigen-specific memory B cell responses; and, the innate immune responses to each of the TLR receptor immunostimulants.

Parasitological testing will include microscopic fecal egg detection by a qualified saline flotation technique, fecal egg counts by the McMaster method, fecal PCR for hookworm DNA, and peripheral eosinophil counts.

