4. Obtain blood for hematology, biochemistry, antibody and cellular immunology assays.
5. Obtain a urine sample for pregnancy testing (females only). Pregnancy test must be negative to proceed; a positive test will exclude the volunteer from the receiving the CHHI.

6. Record vital signs (blood pressure, oral temperature, and heart rate).
7. Administer the *N. americanus* Larval Inoculum.
8. Observe for at least 1 hour after application of the *N. americanus* Larval Inoculum to evaluate for immediate adverse reactions. During the 1-hour post-application wait period, study staff will:
  - Discuss signs and symptoms of potential Adverse Events (AEs);
  - Discuss proper use of the digital thermometer, skin reaction measurement tool, and subject post-CHHI symptom memory aid, and;
  - Review procedures for fecal sample collection, storage, and transport to the clinic.
9. At the end of the observation period, remove absorbent pad used to apply the Larval Inoculum and place in a screw-top tube for transport to GWU MITM.

Study Day 143 (Visit #16) – Telephone Call

1. Review interim medical history emphasizing any acute signs or symptoms (including entries on the post vaccination symptom memory aid).
2. Collect concomitant medication information.

Study Day 147 (Visit #17)

1. Perform basic history and physical exam (including larval application site), emphasizing examination of any acute complaints.
2. Record vital signs.
3. Obtain blood for antibody and cellular assays.
4. Review subject post-CHHI symptom memory aid.

Study Day 154 (Visit #18)

1. Perform basic history and physical exam (including larval application site), emphasizing examination of any acute complaints.
2. Record vital signs.
3. Review and collect post-CHHI symptom memory aid.
4. Give subject two weekly post-CHHI symptom memory aids.
5. Obtain blood for hematology, biochemistry, antibody and cellular assays.

Study Day 175 (Visit #19)

1. Perform basic history and physical exam (including larval application site), emphasizing examination of any acute complaints.
2. Record vital signs.
3. Collect prior weeks' weekly symptom memory aids and give a weekly GI symptom memory aid.
4. Obtain blood for hematology, antibody and cellular assays.
5. Obtain fecal sample for parasitological testing.

Study Day 182 (Visit #20)

1. Perform basic history and physical exam, emphasizing examination of any acute complaints.
2. Record vital signs.

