#### **5.7.5.6 Clinical Laboratory Parameters**

Laboratory evaluation results and changes from baseline will be summarized descriptively by visit using the Safety Population. Unless otherwise specified, all continuous laboratory data will be summarized using descriptive statistics (n, mean, standard deviation (SD), median, minimum, and maximum) for each scheduled study assessment as well as change from baseline and percentage change from baseline [if applicable] by parameter class (hematology and biochemistry).

Hematology, chemistry, rheumatoid factor (RF) and anti-double strand DNA (anti-dsDNA) antibody data will be summarized by displaying shifts from baseline value (Normal/Abnormal) to subsequent assessment after administration of study product.

Safety laboratory data will be listed by visit for each parameter and subject and summarized by Vaccine Group and placebo. All abnormal values that met the definition of an AE as per the protocol will be flagged on the listing.

Hematology parameters includes WBC, Hemoglobin, Platelet Count, Absolute Neutrophil Count and Absolute Eosinophil Count

Biochemistry parameters includes ALT and Creatinine.

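### The SAP's only laboratory baseline precedes the first vaccination, so the post-challenge change and shift tables combine the vaccination and CHHI phases and give no change from the pre-challenge value

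*SAP*

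**What the plan says.** SAP 5.2 fixes the reference: "Baseline is defined as the latest non-missing assessment (whether from scheduled or unscheduled) prior to the first dose administration of the study vaccine", with room for exceptions stated elsewhere. Changes follow directly: "The change from baseline values will be calculated as post baseline value minus the baseline value".

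SAP 5.7.5.6 then applies this: "Laboratory evaluation results and changes from baseline will be summarized descriptively by visit using the Safety Population". It adds percent change where applicable. For hematology, chemistry, rheumatoid factor (RF) and anti-dsDNA it plans tables "displaying shifts from baseline value (Normal/Abnormal) to subsequent assessment after administration of study product". It names no other baseline. It also plans a listing of safety laboratory values by visit, parameter and subject.

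The protocol gives two exposures in sequence: vaccine or saline on Days 0, 56 and 112, then larvae on Day 140. Protocol 7.3, Study Day 140 (Visit #15), places this step before the larvae are applied: "Obtain blood for hematology, biochemistry, antibody and cellular immunology assays". Protocol 9.2.1 counts CHHI as a study product, and 9.3.4 gives it its own AESIs. The Protocol Summary lists among the parasitological tests "fecal PCR for hookworm DNA, and peripheral eosinophil counts". For IgG, Protocol 11.4 plans percent change from the day of CHHI; the SAP gives the laboratory data no equivalent reference.

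**The concern.** A change from baseline is easiest to read when baseline comes just before the exposure of interest. Here every change tabulated after Day 140 spans both exposures. A hemoglobin or eosinophil change at Day 175 is the sum of whatever happened from Day 0 to Day 140 and whatever happened after the larvae. In the shift tables, a value that became abnormal during vaccination and stayed abnormal counts again as a shift from baseline at each later visit.

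At stake is the descriptive safety picture of the challenge phase. Hemoglobin matters because anemia after CHHI is an AESI. Eosinophils matter because the protocol treats them as a parasitological readout. All four groups are challenged, so the within-subject change from a pre-challenge value is the most direct descriptive view of what follows the larvae.

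**Working it through.** **1. Reproduce the blood volumes (Protocol Appendix A).**

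- Vaccination phase: 22+72+50+72+72+50+72+72+50+72 = 604 mL, the stated cumulative figure at Day 126.
- CHHI phase: 67+10+67+62+62+2+2+62+2+2+62+62+15+10 = 487 mL.
- Total: 604+487 = 1091 mL, as stated in Protocol section 7.

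**2. What lies between the SAP baseline and the challenge.**

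- Time: 140/7 = 20 weeks.
- Doses: three (Days 0, 56, 112).
- Scheduled draws from Day 0 through Day 126: 604 − 22 = 582 mL. The Day 0 draw of 72 mL contains the usual baseline sample; without it, 582 − 72 = 510 mL.

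**3. Study blood between the reference sample and later CBCs.** Each figure counts the draw at the reference visit and every draw before the later visit.

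| Later CBC | From Day 0 sample (SAP) | From Day 140 sample | Pre-challenge share of the SAP span |
|---|---|---|---|
| Day 154 | 582+67+10 = 659 mL | 67+10 = 77 mL | 582/659 = 88% |
| Day 175 | 659+67 = 726 mL | 77+67 = 144 mL | 582/726 = 80% |
| Day 280 | 582+338 = 920 mL | 338 mL | 582/920 = 63% |

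The 338 mL is 67+10+67+62+62+2+2+62+2+2. Without the Day 140 draw itself it is 338 − 67 = 271 mL.

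**4. What the planned tables do and do not give.** For one subject let D140 = Y140 − Y0 and D154 = Y154 − Y0.

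- Mean: mean(D154) − mean(D140) = mean(Y154 − Y140), provided the same subjects have both values. The mean change from Day 140 is then recoverable.
- SD: Var(Y154 − Y140) = Var(D154) + Var(D140) − 2·Cov(D154, D140). The covariance is not tabulated, so the SD is not recoverable.
- Percent change: the denominator becomes Y140 instead of Y0, so group summaries of percent change from Y0 do not convert.
- Shift: the baseline-by-Day 140 and baseline-by-Day 154 tables do not determine the Day 140-by-Day 154 table.

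**5. Whether the same subjects have both values.** The documents do not secure this.

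- The Safety Population (SAP 5.3) needs only one dose. Under Protocol 6.3, subjects who miss CHHI are still followed for the duration of the study, so they can enter rows that read as post-challenge. With 12 per group, one or two such subjects can move a mean.
- The Day 297 CBC is taken only in subjects with eosinophilia after CHHI (Protocol 7.3; Appendix A). Subtracting group means there compares a selected subset with the whole group.

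**6. Which markers have a Day 140 value.** CBC, ALT and creatinine do. ALT and creatinine have one scheduled post-challenge measurement, Day 154. RF and anti-dsDNA are not drawn on Day 140; the last draw before challenge is Day 126.

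**The case against.** The strongest reply is that the information is already in the output. SAP 5.7.5.6 summarizes results as well as changes, by visit, and Day 140 is a visit. A fall before the challenge shows in the Day 140 row, and the listings give each subject's values. Protocol 11.4 asks for laboratory trends over time, which needs no second baseline. These are descriptive safety tables, and the table shells are in a separate document (SAP section 10). The definition itself leaves room for an exception: "prior to the first dose administration of the study vaccine, unless otherwise stated". Most of this stands. It limits the point to the change, percent-change and shift tables. It does not supply the SD or the shift from Day 140, and the text available states no exception.

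A reader might infer more than the documents support:

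- *That the analysis cannot show the effect of CHHI.* The by-visit summaries and listings include Day 140.
- *That phlebotomy or a CpG effect biases comparisons between groups.* The draw schedule is the same in all groups, so its effect is expected to cancel between them. Vaccine effect can enter only Groups 1–3. Protocol 2.3.1.2 describes the white-cell and platelet falls as transient, within two weeks of other CpG preparations; the challenge comes four weeks after dose 3.
- *That the baseline choice affects anemia reporting*, for example because only 11.1 − 10.2 = 0.9 g/dL separates the lowest eligible female hemoglobin from the AESI range. The AESI and the Table 5 grades use absolute values, so baseline cannot change who meets them.
- *That a Day 140 baseline would isolate CHHI.* Study draws continue, and no group is unchallenged.

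**Conclusion.** The point holds as a moderate gap in descriptive safety reporting. After Day 140 the planned change, percent-change and shift tables span 20 weeks, three doses and 582 mL of scheduled draws (510 mL without Day 0) that precede the larvae. They may also include subjects who never received larvae. They omit the within-subject change from the pre-challenge value, its SD, and the shift from the pre-challenge category. By-visit results, laboratory AE grades, the anemia AESI and the primary efficacy analysis are unaffected.

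The volumes assume that every scheduled draw is taken. No size in g/dL is claimed, because the documents give no figure for the effect of these draws on hemoglobin. The conclusion also assumes that the separate table shells do not already define a challenge-phase baseline; if they do, SAP 5.2 should say so.

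**What to change.** In SAP 5.2, add a CHHI baseline: the last non-missing value before larval application, normally Day 140.

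In SAP 5.7.5.6, for assessments after larval application, report change, percent change and shift in the CBC parameters, ALT and creatinine from the CHHI baseline, among subjects who received larvae. Keep the existing tables from the pre-dose-1 baseline alongside. Leave RF and anti-dsDNA on the pre-dose-1 baseline, since they are not drawn on Day 140.

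In the report, note that study draws from Day 140 onward (up to 338 mL before the Day 280 sample) remain in the CHHI-phase change and that there is no unchallenged control.

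The cost is SAP wording, one derived variable and a small set of added tables. No new data or visits are needed.

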### **5.3 Analysis Populations**

**All Subjects:** All subjects will include the subjects who signed the informed consent form.

**Randomized Population:** The randomized population will include all subjects who were randomized to any one of the groups.

**Safety Population:** The safety population will include all randomized subjects who have received at least one dose of study vaccine. This population will be used to summarize safety variables and will summarize subjects as vaccinated.

**Immunization Population:** The immunization population will include all randomized subjects who received all three study vaccinations.

**Per Protocol Population:** The per protocol population will include all randomized subjects who received all three study vaccinations and CHHI and completed the study without any major protocol deviations or completed the study with a protocol deviation(s) having no significant impact according to Investigator's assessment.

### **5.4 Protocol Deviations**

A separate listing will be provided with deviation type and description.

### **5.5 Coding Dictionaries Used**

Adverse events will be coded using Medical Dictionary for Regulatory Activities (MedDRA) version 23.0 (or higher). Prior & concomitant medications will be coded using World Health Organization-Drug Reference List (WHO-DRL) (Version: WHODRUG GLOBAL B3 March 1, 2019) and by Anatomical Therapeutic Chemical (ATC) level 4 (or higher).

### **5.6 Study Product Administration and Accountability**

The number and percentage of subjects that received the study product will be summarized by Vaccine Group using the Safety Population.

The exposure to study product will be summarized for total number of doses administered at vaccination and post CHHI visits, using the Safety Population.

A separate listing will be provided with study product administration information including date and time of dosing, dose administered and comment in case dose was not administered.

### **5.7 Analysis Methods**

#### **5.7.1 Disposition**

The number and percentage of subjects who entered the study, were randomized and received the first dose of study product, and those who completed the study will be presented, together with the number and percentage of subjects who prematurely discontinued from the study along with reasons for study discontinuation. Additionally, subjects included in the Randomized Population, Safety Population, Immunization Population and Per Protocol Population will be summarized by Vaccine Group using all subjects.

A listing of each subject's analysis population (Randomized Population, Safety Population, Immunization Population and Per Protocol Population), disposition and reason for discontinuation will be listed.

### **5.7.2 Demographic and Baseline Characteristics**

Demographic and baseline characteristics (gender, ethnicity, race, age [years] will be summarized by Vaccine Group using descriptive statistics for subjects in the Randomized Population. Qualitative variables (gender, ethnicity, race) will be summarized using frequencies and percentages while quantitative variables (age) will be summarized using mean, standard deviation (SD), median, minimum, and maximum.

Individual subject listings of demographic and baseline data will be presented for the Randomized Population.

### **5.7.3 Prior and Concomitant Medications**

Concomitant medications will be summarized by Vaccine Group using the Safety Population.

Concomitant Medications will be coded using World Health Organization-Drug Reference List (WHODRUG GLOBAL B3 March 1, 2019) and will be categorized by preferred name and ATC level 4 class per WHO.

Individual subject listings of all concomitant medications will be presented for the Safety Population.

### **5.7.4 Primary and Secondary Analysis**

#### **5.7.4.1 Primary Endpoint Analysis**

The primary efficacy endpoint analysis of proportion of subjects with detectable hookworm eggs in fecal samples, at any time point post-CHHI, will be summarized using frequency counts and percentages as a descriptive measure at time points post-CHHI for all vaccination groups.

Along with the summaries for any time points post-CHHI, the proportion of subjects with detectable hookworm eggs in fecal samples will be summarized as a descriptive measure by study group at each time point.

The proportion of subjects with detectable hookworm eggs in each of the vaccination groups (Groups 1, 2 and 3) will be compared to the proportion of subjects in the placebo control group (Group 4) using a two-sided Fisher exact test. The p-values for the pairwise comparison of proportions of subjects in the vaccination groups (Group 1, 2 and 3) and placebo group (Group 4) will be reported. No adjustments for multiple comparisons will be made and therefore, the reported p-values will have to be interpreted with caution.

The proportion of subjects with at least one injection site AE and the frequency of the AE grouped by PT will be compared by *Na*-GST-1 vaccine formulation and placebo. The null hypotheses that the type and number of adverse events is the same across all groups will be tested using Fisher's exact test.

Laboratory results (haematological and clinical chemistry) will be descriptively examined and any clinically significant values for individuals will be reported.

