Recruitment and enrollment into the study will occur on an ongoing basis, with each group being recruited and vaccinated in sequence.

48 subjects will be enrolled into 4 groups of 12:

[figure not shown]
Subjects will be enrolled sequentially and upon enrollment will be randomized to one of the following IP assignments in a double-blind fashion:

- Group 1 IP allocation (n=12 subjects):
  - 12 subjects will receive 100 $\mu$ g Na-GST-1/Alhydrogel® delivered by IM injection in the deltoid muscle.
- Group 2 IP allocation (n=12):
  - 12 subjects will receive Na-GST-1/Alhydrogel® plus 500 $\mu$ g CpG 10104 delivered by IM injection in the deltoid muscle.
- Group 3 IP allocation (n=12):

- 12 subjects will receive Na-GST-1/Alhydrogel® plus 5µg AP 10-701 delivered by IM injection in the deltoid muscle.
- Group 4 IP allocation (n=12):
  - 12 subjects will receive sterile saline delivered by IM injection in the deltoid muscle

**Estimated Time to Complete Enrollment:** 6 months

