## 2.2 Rationale

### 2.2.1 Rationale for the Study

A product that combines Na-GST-1 shows promise as an effective hookworm vaccine because vaccination of laboratory animals with recombinant Na-GST-1 results in significant protection from challenge infections (29, 37). Therefore, vaccination of humans with recombinant Na-GST-1 holds promise for inducing protection against this infection, particularly the moderate and heavy intensity infections that are associated with clinical sequelae such as intestinal blood loss and iron-deficiency anemia. The Sabin Vaccine Institute has sponsored a series of Phase 1 trials of the Na-GST-1 candidate antigen in healthy adult volunteers from hookworm endemic areas (rural Brazil and Gabon) and non-endemic areas (urban Brazil and USA). As of May 1, 2017, regulatory sponsorship of these vaccine candidates has been transferred to the Baylor College of Medicine (Houston, TX). These trials have tested three different formulations of Na-GST-1: adsorbed on Alhydrogel®, plus the addition of two different TLR agonist immunostimulants to the Alhydrogel® formulation, AP 10-701 and CpG 10104. These Phase 1 trials have demonstrated that all three formulations are well tolerated, have not resulted in significant adverse events, and induce antigen-specific IgG antibodies.

Since there are no known immune correlates of protection against natural hookworm infection, it is unclear how the immunogenicity observed in the Phase 1 trials of Na-GST-1 will translate into efficacy. Following the traditional pediatric vaccine clinical development pathway, the next steps would be to conduct age de-escalation Phase 1 trials into children, followed by large pediatric Phase 2 and 3 field trials. Given the transmission dynamics of hookworm even in highly endemic areas, it is estimated that it would take at least two years and require over 1000 children to be enrolled into a Phase 2 proof-of-concept trial of a single vaccine candidate in which the main endpoint would be mean fecal egg count. Given the length of time, the effort, and the cost involved, it would not be feasible to conduct multiple such Phase 2 trials of the

different vaccine formulations that have progressed past the Phase 1 stage. Therefore, it is critical that a new paradigm is developed in which an estimate of efficacy can be made early in development so that different candidate formulations can be compared and the most promising selected for advancement into pediatric testing.

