## 5.3 Treatment Assignment Procedures

### 5.3.1 Randomization Procedures

Eligible volunteers will be asked to come to the clinic on their scheduled day of enrollment into the study (Day 0). After undergoing a clinical interview and directed physical examination to ensure that they remain eligible for participation in the study, that they have had blood collected for safety clinical laboratory and baseline immunogenicity assessments, and that females have had a urine pregnancy test performed that is documented to be negative, volunteers will be randomized and enrolled in the order that they present for vaccination.

Within each group, randomization will be done through use of a randomization code, furnished to the study vaccine manager by the study statistician. Access to the randomization list will be exclusively limited to the study vaccine manager and assistant. Between vaccination days, the randomization list will be stored in a locked cabinet in the GW MFA Investigational Drug Service pharmacy or the office of the study vaccine manager. The study vaccine manager and assistant will be unblinded, but will not be involved in further evaluation of study subjects or assessment of adverse events. Volunteers will not be considered enrolled in the study until they have received their first dose of vaccine. In the event that a volunteer is randomized but not enrolled on the day of first vaccination, they will be replaced with an eligible alternate. Enrolled subjects that leave the study for any reason following first vaccination will not be replaced.

Vaccine/placebo assignment will be done by block randomization. That is, for each block of 4 subjects who are sequentially enrolled into the trial, 1 will be assigned to receive Na-GST-1/Alhydrogel®, 1 to Na-GST-1/Alhydrogel® plus CpG 10104, 1 to Na-GST-1/Alhydrogel® plus AP 10-701, and 1 to sterile saline placebo.

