### 11.2 Sample Size Considerations

Sample size considerations are based on the proportion of subjects with detectable hookworm eggs at any time, as measured by the saturated saline flotation technique. The primary analysis of the proportions will consist of comparing the proportion in each of the three *Na*-GST-1

intervention groups to the proportion in the placebo control group (group 4) using a one-sided Fisher exact test, for a total of three comparisons. The Holm-Bonferroni procedure will be used to control the familywise error rate at 0.05. Based on the results from the initial CHHI trial that was conducted at GWU (NCT01940757), we expect an infected proportion of 90% in group 4 (i.e., infectivity controls), and a proportion less than 20% in at least one of the intervention groups. At alpha=0.05/3, this yields a power of 87.7%. The power is 73.2% for an infection rate of 30% in intervention and 96.3% for an infection rate of 10%.

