### 11.4 Final Analysis Plan

The purpose of this trial is to estimate vaccine efficacy as assessed by CHHI, adverse event rates and patterns of immune responses as well as to compare these rates and patterns between the investigational Na-GST-1 vaccine formulations.

This section briefly describes the statistical methods to be used; a detailed analytical plan will fully describe the methods. The analytical plan will discuss the planned approaches to missing data. Deviations from the original analytical plan will be thoroughly documented and reported to the Sponsor.

Descriptive and hypothesis-testing approaches will be used to meet the protocol objectives as stated in **Section 3**. Estimates will be presented with their 95% confidence intervals. Formal statistical tests, as outlined below, will be used to compare the different Na-GST-1 vaccine formulations, as compared to saline placebo. Statistical tests will use a significance level of 5% (either two-sided or one-sided, depending on the analysis being conducted; this will be specified *a priori*).

**Primary Objective #1:** To compare the impact of vaccination with Na-GST-1/Alhydrogel® delivered with or without AP 10-701 or CpG 10104 on controlled human hookworm infection (CHHI) with *N. americanus* larvae in healthy, hookworm-naïve adults, as determined by the presence of eggs using a qualified flotation technique.

*Primary Outcome #1 Measure:*

The following parameters will be evaluated for each formulation of Na-GST-1:

1. Proportion of subjects with detectable hookworm eggs, at any time point, in fecal samples, as determined by microscopy using the qualified saline float technique.

*Analysis Plan:*

- a. The proportion of participants with detectable hookworm eggs in fecal samples by microscopy, at any time point post-CHHI, will be summarized as a descriptive measure by study group.

IRB NUMBER: 121643

IRB APPROVAL DATE: 11/17/2025

- b. The proportion of participants with detectable hookworm eggs in fecal samples by microscopy will be summarized as a descriptive measure by study group at each time point.

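### The protocol sets out to estimate efficacy and compare formulations, but the SAP's primary infection analysis has no effect estimate with a confidence interval, and neither document plans an infection estimate between formulations

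*SAP*

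**What the plan says.** **The aim.** Protocol 2.2.1 argues for an early efficacy estimate so that "different candidate formulations can be compared and the most promising selected for advancement into pediatric testing". Protocol 11.4 opens by saying the trial is to estimate vaccine efficacy, adverse event rates and immune responses, "as well as to compare these rates and patterns between the investigational Na-GST-1 vaccine formulations". It then sets a general rule: "Estimates will be presented with their 95% confidence intervals".

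**The limit on the aim.** Protocol 11.1, repeated in SAP 5.1, says the study is not built to test small efficacy differences between formulations. It is meant to indicate an impact on infection and to detect large differences.

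**The primary analysis.** Protocol 11.2 and 11.4 item c compare each of Groups 1, 2 and 3 with Group 4 by a one-sided Fisher exact test with Holm-Bonferroni at 0.05. SAP 5.7.4.1 makes the same three comparisons with a two-sided Fisher test and no multiplicity adjustment. Its output is counts and percentages by group, overall and by time point, followed by "The p-values for the pairwise comparison of proportions of subjects in the vaccination groups (Group 1, 2 and 3) and placebo group (Group 4"), with a warning to read the p-values with caution. It names no effect measure and no interval. Neither document contrasts infection among Groups 1, 2 and 3.

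**Other endpoints.** SAP 5.7.4.2 plans differences with 95% CIs for egg counts and for IgG, each against placebo. SAP section 7, on changes from the protocol, does not mention leaving intervals out of the primary analysis.

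**The concern.** Followed exactly, SAP 5.7.4.1 does not produce the quantity that protocol 11.4 gives as the purpose: an efficacy estimate per formulation with its uncertainty, and a comparison of those estimates. Whoever chooses a formulation for pediatric trials would have four percentages, each from 12 subjects or fewer, and three p-values against saline. The percentages give an order with no measure of its reliability. The p-values answer a different question, whether each formulation differs from saline, and two formulations with the same true effect can land on opposite sides of any threshold by chance. The primary endpoint would also be reported less fully than the secondary ones.

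**Working it through.** **Inputs**
- Size: "48 subjects will be enrolled into 4 groups of 12" (protocol, Description of Study Design).
- Allocation 1:1:1:1: "for each block of 4 subjects who are sequentially enrolled into the trial, 1 will be assigned to receive" each regimen (protocol 5.3.1).
- Placebo infection: "we expect an infected proportion of 90% in group 4 (i.e., infectivity controls" (protocol 11.2). Vaccine-group scenarios there: 10%, 20% and 30%.
- Dropout: no rate is given, and "Enrolled subjects that leave the study for any reason following first vaccination will not be replaced" (protocol 5.3.1). I assume none, so the intervals below are the narrowest the design can give.
- Alpha: protocol, one-sided 0.05 with Holm. The only alpha in the SAP is about 0.1, in section 3.1; SAP 5.7.4.1 sets no threshold.

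**1. The plan's own power.** Sum the binomial probabilities over all 13 x 13 outcomes for which the one-sided Fisher p is at most 0.05/3, with placebo at 90%:

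| Vaccine rate | Stated | Recomputed |
|---|---|---|
| 10% | 96.3% | 97.6% |
| 20% | 87.7% | 88.8% |
| 30% | 73.2% | 74.1% |

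These agree within 2 points. They apply to vaccine against saline only.

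**2. What effect estimates would show.** Suppose placebo is 11/12 (my assumption). Risk difference = x/12 - 11/12; vaccine efficacy = 1 - (x/12)/(11/12) = 1 - x/11.

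| Vaccine | Risk difference (Newcombe 95% CI) | Efficacy | Two-sided p |
|---|---|---|---|
| 2/12 | -75 points (-89 to -36) | 1 - 2/11 = 82% | 0.0006 |
| 5/12 | -50 (-73 to -12) | 1 - 5/11 = 55% | 0.027 |
| 6/12 | -42 (-67 to -5) | 1 - 6/11 = 45% | 0.069 |

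**3. Between two formulations.** 6/12 - 5/12 = 1/12 = 8 points. The 95% CI is -30 to +44 by the score method and -28 to +42 by Newcombe; Fisher p = 1.0.

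**4. How reliable a ranking on percentages is.** Choosing the lowest observed rate, with ties split at random, finds the truly best formulation with probability 57% at true rates 20/30/30%, 77% at 20/40/40% and 90% at 20/50/50%.

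**5. Mixed verdicts when the formulations are identical.** Let q_c be the chance that one formulation is significant when placebo has c infected. Without adjustment, the chance that one or two of three are significant is the sum over c of P(c) x [1 - q_c^3 - (1 - q_c)^3]. For Holm, enumerate all four counts.

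| True rate | Protocol: one-sided, Holm 0.05 | SAP: two-sided 0.1 | Assumed: two-sided 0.05, unadjusted |
|---|---|---|---|
| 20% | 4% | 5% | 13% |
| 30% | 15% | 18% | 34% |
| 40% | 28% | 39% | 52% |
| 50% | 33% | 53% | 53% |

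The 40% and 50% rows lie outside the protocol's scenarios.

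**6. Would testing formulations directly help?** Two-sided Fisher power at 0.05 is 9% for 20% against 40% and 21% for 20% against 50%. It would not; estimates with intervals are the workable output.

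**The case against.** The case against has five parts.

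- **Saline is the stated comparator.** Protocol 3.2.1 defines the primary outcome against saline, and the first hypothesis in 11.1 is against placebo; the between-formulation hypotheses there concern immune responses. Section 11.1 disclaims small differences. This stands as a reason not to test formulations against each other. It is not a reason to leave the differences unestimated when 11.4 names comparison as a purpose.
- **The numbers can be derived.** With four groups of 12, anyone can compute a difference and an interval from the tabulated counts, and the SAP is to be read with the protocol, which has the general CI rule. That is true, so the gap is one of pre-specification. But the rule does not name the effect measure, the interval method or the contrasts.
- **Other analyses cover part of it.** SAP 5.7.4.2 has a log-rank comparison of time to patency between groups, and a logistic model of infection giving odds ratios with 95% CIs. The log-rank test gives no infection difference. The logistic model is exploratory and includes IgG response, which vaccination itself changes, so its group terms are not vaccine efficacy.
- **Table shells are separate.** SAP section 10 puts the list of tables in another document, which may contain intervals. The SAP text does not call for them.
- **A p-value rule is not in the plan.** A reader might infer that the SAP reports only p-values, or that the formulation will be chosen by which p-value crosses a line. Neither is supported. Counts and percentages are also reported, so a ranking is possible. SAP section 1 bases decisions on efficacy, tolerability and safety together. Protocol 2.2.5 has the sponsor review the final report and asks for efficacy of at least one formulation. The 5/12 and 6/12 results are opposite verdicts only at an assumed 5% two-sided level. At about 0.1 both fall below the line. Under one-sided Holm (p = 0.0136 and 0.0343) a split depends on the third formulation.

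**Conclusion.** The concern holds as a gap between stated purpose and planned output. SAP 5.7.4.1 pre-specifies no risk difference or vaccine efficacy with a CI for infection, and neither document pre-specifies an infection estimate between formulations, although protocol 11.4 promises intervals and names the comparison as a purpose. Its size is best seen in the width of the missing intervals: about 70 points or more for two formulations with results near 50%. Mixed verdicts among identical formulations are a modest risk at the documents' own alphas (about 4-5% at a true rate of 20%, 15-18% at 30%). The figures of 13% and 34% need an unadjusted two-sided 5% threshold that neither document sets. All of this assumes 12 evaluable subjects per group, 90% placebo infection and independent binomial outcomes. It is worth correcting, but it does not undermine the comparison with saline.

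**What to change.** In SAP 5.7.4.1, and in protocol 11.4 primary analysis item c:

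1. For each formulation against saline, report the risk difference and vaccine efficacy (1 minus the risk ratio), with exact or score 95% CIs. Name the interval method.
2. Report the infection risk difference with a 95% CI for Group 2 vs 1, Group 3 vs 1 and Group 2 vs 3, as estimates only, with no tests.
3. State that formulations are compared on these estimates and intervals.

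This needs a few sentences and some table rows, and no new data. It adds no hypothesis tests and so uses no alpha. The downside is that the between-formulation intervals will be visibly wide.
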